## 4 ESTIMANDS

Not Applicable.

Property of Haleon - Confidential

May not be used, divulged, published or otherwise disclosed without the consent of  
Haleon

Clinical Protocol Template, TMF-187821, v11.0. Parent SOP: **CCI**

## 5 STUDY DESIGN

This prospective open-label, single-arm, multi-country (US and EU) real-world evidence study (RWE) study, conducted in a hybrid format focusing on assessing the impact of Voltaren Gel on functional mobility and quality of life (QoL) in individuals with mild/non-serious osteoarthritis (OA) of the knee.

[figure not shown]
The target population comprises adults aged between 40 and 85 years, diagnosed with knee mild/non-serious osteoarthritis and self-reporting pain at the time of recruitment. Approximately 195 subjects are expected to be enrolled in the study, with an anticipation that around 147 of these subjects will successfully complete the entire study.

In this hybrid study design, participants will be required to physically attend on-site visits for screening, baseline assessments, and end-of-study evaluations. However, for the remainder of the study period, data collection will be executed remotely following the guidelines provided by **CCI** utilising an (electronic) eDiary system.

In the EU, two variants of Voltaren Gel are available, namely 1.16% and 2.32% DDEA. During the screening and enrolment process, the investigator will assess the subjects' product preference as well as the need and the severity of osteoarthritis (OA) to determine and dispense the appropriate percentage of gel. The aim is to include a minimum of 25 patients utilising the 1.16% Voltaren Gel to enable understanding of real-world usage for the 1.16% Voltaren variant.

Advertisements approved by (Investigation Review Board) IRBs/ Ethics Committee (ECs) and investigator databases may be used as recruitment procedures. Use of EC approved generic, pre-screening questionnaire to assess basic subject characteristics to determine general eligibility for this study is allowed.

Haleon will review and approve the content of any study recruitment materials directed to potential study subjects before such materials are used.

Property of Haleon - Confidential

May not be used, divulged, published or otherwise disclosed without the consent of  
 Haleon

Clinical Protocol Template, TMF-187821, v11.0. Parent SOP: **CCI**

### 5.1.1 Limitations of the study

Given the natural course of OA and pain, data collected during this study may be confounded by the natural course of the disease. Within 24 hours of pain onset, subjects generally report an increase in the severity and number of symptoms they experience.

Given the natural course of the disease, ensuring subjects have access to treatment when OA symptoms are present will allow for subsequent quality of life (QoL) data to be captured, reducing the influence of confounding variables.

Subjects may likely be using other over-the-counter antipyretics/analgesics for severe pain, which may influence their overall Actigraph and QoL data and confound the effect of Voltaren. During this study, subjects will be prompted to report medications they take for symptom relief, along with any changes in medication over the course of their study participation, to better understand the results.

Actigraph is a clinically approved, research-grade, and validated device. It boasts commendable accuracy and applicability in its device and algorithm, ensuring reliable data quality. While some limitations of its usage in a real-world environment may exist, the device's robust design minimises the likelihood of false data, affirming its overall dependability. However, subjects may not be comfortable wearing a wearable device continuously as well as subject non-wear compliance and user related errors may have an impact on the data collected.

At the start of the study, site staff will be given training by Actigraph or relevant trained personnel or through online videos on how to use the device (see tutorial link in appendix), with training on how to use and wear the device appropriately. After receiving training, site staff can then appropriately train subjects, particularly during the dispensing of the product.

### 5.2 Justification for Dose

The study plans to collect and evaluate data from all Voltaren topical marketed doses. Dosing instructions will be followed as listed on the study product commercial label.

### 5.3 End of Study and Clinical Trial Definition

A subject is considered to have completed the study if they have completed all procedures and assessments of the study including the last scheduled procedure shown in the [Schedule of Activities](#).

Subjects will have the option to discontinue treatment at their discretion, if they determine they no longer want treatment. The reasons for discontinuing treatment will be captured whenever possible. The end of this study is defined as last visit of the last subject. At the end of the study each study subject shall complete an exit survey as detailed in the appendix.

## 6 STUDY POPULATION

### 6.1 Type and Planned Number of Subjects

Adults between 40-85 years of age with a diagnosis of knee osteoarthritis and self-reported pain at recruitment will undergo screening for inclusion in the study. Anticipating a dropout rate of approximately 25%, the trial aims to enrol a total of 195 eligible subjects, with an expected completion rate of approximately 147 study participants.

Eligibility criteria for participation in the study include adult subjects diagnosed with knee osteoarthritis, supported by radiological evidence obtained within the last three years. Additionally, participants must self-report knee pain, registering a score of  $\geq 40$  mm and  $\leq 70$  mm on the pain intensity visual analogue scale (VAS). Prospective participants must express willingness and ability to adhere to scheduled visits, follow an on-label Voltaren gel use, comply with other study procedures, and commit to using Voltaren gel for up to three weeks. For comprehensive details, refer to the inclusion and exclusion criteria provided below.

A Screened subject is one who has agreed to participate in the clinical study following completion of the informed consent process directly or via their legally authorised representative.

An enrolled subject is one who has agreed to participate in the clinical study following completion of the informed consent process directly or via their legally authorised representative and successfully met eligibility criteria to proceed beyond the screening visit as applicable for the protocol design.

This study can fulfil its objectives only if appropriate subjects are enrolled. The following eligibility criteria are designed to select subjects for whom participation in the study is considered appropriate. All relevant medical and non-medical conditions should be taken into consideration when deciding whether a subject is suitable for this protocol.

Subject eligibility to participate in the clinical study should be reviewed and documented by an appropriate member of the investigator's study team before subjects are included in the study.

### 6.2 Inclusion Criteria

An individual must meet all the following inclusion criteria to be eligible to be included into the study:

1. Subject provision of a signed and dated informed consent document indicating that the subject has been informed of all pertinent aspects of the study before any assessment is performed.
2. Subject is male or female who, at the time of screening, is between the ages of 40 and 85 years, inclusive.

Property of Haleon - Confidential

May not be used, divulged, published or otherwise disclosed without the consent of  
Haleon

Clinical Protocol Template, TMF-187821, v11.0. Parent SOP: **CCI**

3. A subject who is willing and able to comply with scheduled visits, on-label Voltaren Gel use plan, and other study procedures.
4. A subject willing to wear Actigraph continuously 24/7 for the study period.
5. A subject in good general and mental health.
6. A subject with diagnosed knee mild/non-serious osteoarthritis, proven via radiological evidence collected within the last 3 years (Any documentation that indicates mild/moderate OA is acceptable – such as Kellgren/Lawrence (K/L) method of assessment).
7. A subject with self-reported knee pain, with a score of  $\geq 40$  mm  $\leq 70$ mm on the pain intensity visual analogue scale at the time of Informed Consent Form (ICF) signature.
8. A subject willing to use Voltaren Gel for up to 3 weeks.
9. A subject of potential childbearing willing to follow an effective method of contraception (as listed below in section 11.7) from the time of screening (post consent prior to the use of product) and up to end of study visit.

### 6.3 Exclusion Criteria

An individual who meets any of the following exclusion criteria will be excluded from the study:

1. A subject who is an employee of the investigational site, either directly involved in the conduct of the study or a member of their immediate family; or an employee of the investigational site otherwise supervised by the investigator; or a Haleon employee directly involved in the conduct of the study or a member of their immediate family.
2. A subject who has participated in other studies (including non-medicinal studies) involving investigational product(s) within 1 month prior to study entry and/or during study participation.
3. A subject with, in the opinion of the investigator or medically qualified designee, an acute or chronic medical or psychiatric condition or laboratory abnormality that may increase the risk associated with study participation or investigational product administration or may interfere with the interpretation of study results and, in the judgment of the investigator or medically qualified designee, would make the subject inappropriate for entry into this study.
4. A subject with confirmed rheumatologic disease
5. A subject who has experienced trauma to the knee within the last 2 months that resulted in pain and/or swelling.
6. A subject that has been administered local steroids or other NSAIDs injections to the knee within the last 6 months.
7. A subject with recent history of major knee injury or surgery.
8. A subject with knee skin area pathological condition which prevents application of product to the skins. Conditions such as: open skin wounds, infections, inflammations, or exfoliative dermatitis conditions.

Property of Haleon - Confidential

May not be used, divulged, published or otherwise disclosed without the consent of  
 Haleon

Clinical Protocol Template, TMF-187821, v11.0. Parent SOP: **CCI**

9. A subject with conditions not limited to the following: Gastrointestinal diseases, asthma, hypertension, myocardial infarction, thrombotic events, stroke, congestive heart failure, impaired renal function, or liver disease as judged by investigator or Site Staff.
10. A subject diagnosed with other relevant medical conditions (e.g., psychiatric, neurological - This excludes subjects with well-controlled depression, anxiety or migraines who are on a stable dose of medication which may be allowed – this is up to the discretion of site staff and investigators).
11. A subject who takes medication relating to above conditions, such as tricyclic antidepressants or anticonvulsants
12. A subject with an active infection.
13. A Female subject who is pregnant at Screening as evidenced by a positive UPT, or intending to become pregnant (see section 11.7 Pregnancy).
14. A subject with use of aspirin, Oral Nonsteroidal Anti-inflammatory Drugs, topical treatment with any NSAIDs, warfarin, ACE inhibitors, cyclosporine, diuretics, lithium or methotrexate, corticosteroids, or other anticoagulant therapy within 30 days of study.
15. A subject with known or suspected intolerance or hypersensitivity to the study materials (or closely related compounds) or any of their stated ingredients, including hypersensitivity to NSAIDs and aspirin triad.
16. A subject with any other acute or chronic illness that could compromise the integrity of study data or place the subject at risk by participating in the study.
17. A subject who, in the opinion of the investigator or medically qualified designee, should not participate in the study.

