Selection of Subjects	
Main Inclusion Criteria:
 
 
• A Subject between the age of 40 and 85 years.
 
• A subject with diagnosed knee mild/non-serious osteoarthritis, proven via radiological evidence collected within the last 3 years.
 
• A subject with self-reported knee pain, with a score of <math>\geq 40</math> mm <math>\leq 70</math>mm on the pain intensity visual analogue scale at the Screening Visit.
 
• A subject willing to use Voltaren Gel for up to 3 weeks.
 
 
Main Exclusion Criteria:
 
 
• A subject with confirmed rheumatologic disease.
 
• A subject who has experienced trauma to the knee within the last 2 months that resulted in pain and/or swelling.
 
• A subject that has been administered local steroids or other NSAIDs injections to the knee within the last 6 months.
 
• A subject with recent history of major knee injury or surgery.
 
• A subject with knee skin area pathological condition which prevents application of product to the skins. Conditions such as: open skin wounds, infections, inflammations, or exfoliative dermatitis conditions.
 
• A subject who is pregnant, lactating or plan to be pregnant or lactating during the study.
 

------------------------------	--

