## Footnotes:

a Actigraph tracker is dispensed at screening visit post consent of patient during enrolment for the study (D -7 – Visit 1). and Voltaren is dispensed immediately post eligibility of the subject at the end of Baseline period (Day 0 – Visit 2).

b The questionnaires such as: Pain Visual Analogue Scale (VAS) / Numeric Rating Scale (NRS), will initially be performed on site during enrolment period (Visit 1) and prior to dispensing of Voltaren (Visit 2), to complete the baseline assessment. Subjects are then required to perform the assessment of NRS, Western Ontario and McMaster University Osteoarthritis index (WOMAC), Karolinska Sleepiness Scale and the EQ-5D-5L Health questionnaire at site prior to dispensing of Voltaren (Day 0 – Visit 2) and then at home during the study period and report the score within the eDiary.

c Adverse Events (AEs) and therefore all Serious Adverse Events (SAEs) will be collected immediately after a subject provides consent to participate in the study by the completion of the Informed Consent Form (ICF).

\* Baseline period will be flexible and last a minimum of 3 days and maximum 7 days to collect sufficient baseline information from study subjects. When pain levels reach  $\geq 40$  mm  $\leq 70$ mm in the VAS/NRS scale, the day before starting the use of Voltaren, study subjects will be prompted to answer relevant questionnaires to assess baseline levels. Site staff to monitor subjects eDiary and dispense Voltaren when patients have ended baseline period. Subjects can also notify site staff when their baseline period has ended to commence the study.

\*\* Study period will last a maximum of 28 days. Study subjects are allowed to stop using Voltaren if they feel that their pain has successfully resolved and do not need to use the product anymore.

\*\*\*Urine test only needed for women of childbearing potential and postmenopausal women who are not surgically sterile. Urine samples are collected to detect the presence of human chorionic gonadotropin (hCG), a hormone produced during pregnancy.

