### **9.1.4 Subject Eligibility**

The investigator and/or medically qualified designee will review inclusion/exclusion criteria, medical history, prior medications to confirm subject eligibility to participate in the clinical study. This will be documented in the eCRF.

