## **11.9 Risks and benefits related to the participation in the clinical trial**

### **11.9.1 Risks related to Voltaren gel**

The Investigational Medicinal Product (IMP), Voltaren gel, is registered and marketed in countries concerned by the study. The IMP will be used in accordance with the indications, posology and safety product information approved.

Voltaren gel is contraindicated in the following circumstances:

- In patients with a known hypersensitivity to diclofenac or to any of the product excipients.
- In patients in whom asthma, angioedema, urticaria, or acute rhinitis are precipitated by acetylsalicylic acid or other non-steroidal anti-inflammatory drugs (NSAIDs).
- During the last trimester of pregnancy and during lactation/breastfeeding.

Special Warnings & Precautions for Use:

The possibility of experiencing systemic adverse events (those associated with the use of systemic forms of diclofenac) should be considered if Voltaren gel is used at a higher dosage or for a longer period of time than recommended.

Voltaren gel should be applied only to intact, non-diseased skin, and not to skin wounds or open injuries. It should not be allowed to come into contact with the eyes or mucous membranes and should not be ingested. Voltaren Emugel can be used with non-occlusive bandages but should not be used with an airtight occlusive dressing.

Interactions with other Medical Products and other Forms of Interaction:

Since systemic absorption of diclofenac from topical application is very low, interactions are unlikely.

Pregnancy & Lactation:

There are insufficient data on the use of diclofenac in pregnant women. Diclofenac should be used during the first two trimesters of pregnancy only if the expected benefit justifies the potential risk to the foetus. As with other NSAIDs, use of diclofenac during the third trimester of pregnancy is contraindicated owing to the possibility of uterine inertia, fetal renal impairment with subsequent oligohydramnios and/or premature closure of the ductus arteriosus.

Property of Haleon - Confidential

May not be used, divulged, published or otherwise disclosed without the consent of  
Haleon

Clinical Protocol Template, TMF-187821, v11.0. Parent SOP: **CCI**

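### The protocol summary excludes lactating women and section 11.9.1 contraindicates use in lactation, but no numbered eligibility criterion names it

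*Protocol*

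**What the plan says.** The protocol deals with lactation and eligibility in several places.

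- **Section 1, Protocol Summary, main exclusion criteria.** Among those excluded is "A subject who is pregnant, lactating or plan to be pregnant or lactating during the study".
- **Section 6.3, exclusion 13.** The corresponding numbered criterion is "A Female subject who is pregnant at Screening as evidenced by a positive UPT, or intending to become pregnant (see section 11.7 Pregnancy". Lactation does not appear.
- **Section 11.7, Pregnancy.** The section that exclusion 13 refers to covers pregnancy testing, contraception and the reporting of pregnancies. It does not mention lactation.
- **Section 11.9.1.** The contraindications include "During the last trimester of pregnancy and during lactation/breastfeeding". The same section commits the trial to the label: "The IMP will be used in accordance with the indications, posology and safety product information approved". Its later paragraph on pregnancy and lactation is softer and allows use in lactation where the expected benefit justifies the risk to the infant.
- **Section 9.1.4.** Eligibility is settled as follows: "The investigator and/or medically qualified designee will review inclusion/exclusion criteria, medical history, prior medications to confirm subject eligibility to participate in the clinical study".
- **Section 1.1, footnote to the urine pregnancy test.** "Urine samples are collected to detect the presence of human chorionic gonadotropin (hCG), a hormone produced during pregnancy".

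The SAP does not restate the criteria. Its section 6.1 defines the enrolled population and screening failures from the inclusion/exclusion eCRF page, and the mITT population also requires that the criteria be met.

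**The concern.** A summary normally shortens the full list. Here the short list contains a safety exclusion that the full list lacks, although section 6.1 sends the reader to the numbered criteria for the details. Sites screen against the numbered list, so a breastfeeding woman whom the summary keeps out is not kept out by any criterion that names her condition.

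What is at stake is the safety of the mother and infant, not the efficacy result. There is also a consequence for traceability. A breastfeeding woman admitted under the numbered list would have no failed criterion recorded on the eCRF page. She would count as eligible in the SAP's enrolled and mITT populations and would not appear in the listings of eligibility failures in SAP section 10.2.1.

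**Working it through.** No formula is involved; the check is a comparison of text.

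**Step 1: read every numbered criterion.** Section 6.2 has 9 inclusion criteria and section 6.3 has 17 exclusion criteria, 9 + 17 = 26. The number naming lactation or breastfeeding is 0 of 26.

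**Step 2: set the contraindications in 11.9.1 against the numbered criteria.**

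| Contraindication in 11.9.1 | Numbered criterion that covers it |
|---|---|
| Hypersensitivity to diclofenac or excipients | Exclusion 15 |
| Aspirin- or NSAID-provoked asthma, angioedema, urticaria or rhinitis | Exclusion 15 (NSAID hypersensitivity, aspirin triad) |
| Last trimester of pregnancy | Exclusion 13 |
| Lactation/breastfeeding | None by name |

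Section 11.9.3 says the criteria were chosen with the approved safety information in mind. For this one item the list does not deliver that.

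**Step 3: see whether another provision closes the gap.**

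- *Urine test.* It detects hCG, so a breastfeeding woman who is not pregnant tests negative.
- *Inclusion 3.* It requires "A subject who is willing and able to comply with scheduled visits, on-label Voltaren Gel use plan, and other study procedures". This excludes her only if the site reasons that on-label use rules out lactation. The conditional-use sentence later in 11.9.1 weakens that reasoning.
- *Exclusions 3 and 16.* They concern medical or psychiatric conditions and illness. Lactation fits neither naturally.
- *Exclusion 17.* This is investigator discretion.
- *Section 6.1.* "All relevant medical and non-medical conditions should be taken into consideration when deciding whether a subject is suitable for this protocol" is a general suitability judgement.
- *Medical history (section 9.1.3).* It covers the last year, including allergies, and does not ask for lactation.

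Each of these may stop such an enrolment. None is a numbered rule that does so by name.

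**Step 4: size.** The documents give no figure from which to estimate how many subjects could be affected. The weight of a single case follows from the planned numbers in section 13.1:

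- share of enrolled subjects: 1/195 = 0.51%
- share of expected completers: 1/147 = 0.68%

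These figures show only that one case cannot matter to the MVPA analysis. They say nothing about likelihood. Entry at 40 to 85 years with radiological knee osteoarthritis makes zero cases plausible. The protocol does, however, expect some women of childbearing potential, since it requires contraception (inclusion 9) and pregnancy testing.

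**The case against.** The strongest reply is that the protocol does contain an explicit exclusion, in the summary, and that section 6.3 is silent on lactation without permitting it. Read as a whole, the document leans towards exclusion: on-label use is required, the label is said to govern, and lactation is a listed contraindication. Enrolment would need a site to overlook all of that. The safety text is also mixed. Section 11.9.1 allows conditional use in lactation and describes systemic absorption from topical use as very low, and section 9.2.2 limits use to 21 days. Finally, the eligibility eCRF page and the screening questionnaire are not reproduced in the documents; if either asks about lactation, the gap has no practical effect.

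Much of this stands. The defect is an exclusion not carried into the operative list, and the sponsor's intention is not in doubt. The probability of a case is low and the risk per case is not shown to be high, although 11.9.1 says it is not known whether topical diclofenac passes into breast milk. The unseen forms could close the gap.

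The reply does not remove the mismatch. Section 9.1.4 has eligibility confirmed against the inclusion/exclusion criteria, medical history and prior medications. The indirect safeguards work only if a site makes the connection itself, and the conditional wording in 11.9.1 points it the other way.

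**Conclusion.** The concern holds. The summary and the contraindication list name lactation, and the 26 numbered criteria and section 11.7 do not. Exclusion 13, applied as written, does not keep out a woman whom the summary says must be kept out.

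The practical size is small: few if any subjects, 0.51% of planned enrolment for each one, and no material effect on the primary analysis. It still merits correction, because it concerns a safety exclusion the sponsor has already chosen.

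Confidence is high on the text. Whether a breastfeeding woman could in fact pass screening assumes that neither the eligibility page nor the screening questionnaire asks about lactation, which cannot be seen from the documents.

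**What to change.** Extend exclusion 13 to match the summary, so that it covers a woman who is pregnant at Screening on a positive urine test, is lactating, or intends to become pregnant or to lactate during the study. Confirm that the Visit 1 eligibility page or screening questionnaire asks women about lactation, and add the question if it does not, because the urine test cannot answer it. Optionally, state in 11.9.1 that the conditional-use wording on lactation does not apply to trial subjects.

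The cost is one phrase at the next amendment and at most one eligibility question. There is no new procedure, and the effect on recruitment is negligible.

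SAP version 2.0 already incorporates decisions from the data review meeting, so enrolment may be over. If it is, the proportionate step is to check that no enrolled woman of childbearing potential was breastfeeding, and to carry the corrected wording into later protocols.
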